9.1.6. Case Report Forms

For each subject consented, an eCRF will be completed by an authorized study staff member whose training for this function is documented according to study procedures. The eCRF should be completed on the day of the subject visit to enable the sponsor to perform central monitoring of safety data. The Eligibility Criteria eCRF should be completed only after all data related to eligibility has been received. Subsequent to data entry, a study monitor will perform source data

verification within the electronic data capture (EDC) system. Original entries as well as any changes to data fields will be stored in the audit trail of the system. Prior to database lock (or any interim time points as described in the clinical data management plan), the investigator will use his/her log in credentials to confirm that the forms have been reviewed, and that the entries accurately reflect the information in the source documents. The eCRF captures the data required per the protocol schedule of events and procedures. System-generated or manual queries will be issued to the investigative site staff as data discrepancies are identified by the monitor or internal Gilead staff, who routinely review the data for completeness, correctness, and consistency. The site coordinator is responsible for responding to the queries in a timely manner, within the system, either by confirming the data as correct or updating the original entry, and providing the reason for the update (eg, data entry error). At the conclusion of the trial, Gilead will provide the site with a read-only archive copy of the data entered by that site. This archive must be stored in accordance with the records retention requirements outlined in Section 9.1.5.

9.1.7. Investigational Medicinal Product Accountability and Return

Where possible, IMP should be destroyed at the site. At the start of the study, the study monitor will evaluate each study center's IMP disposal procedures and provide appropriate instruction for disposal or return of unused IMP supplies. If the site has an appropriate standard operating procedure (SOP) for drug destruction as determined by Gilead Sciences, the site may destroy used (empty or partially empty) and unused IMP supplies as long as performed in accordance with the site's SOP. This can occur only after the study monitor has performed drug accountability during an on-site monitoring visit.

A copy of the site's IMP Disposal SOP or written procedure (signed and dated by the Principal Investigator [PI] or designee) will be obtained for Gilead site files. If the site does not have acceptable procedures in place, arrangements will be made between the site and Gilead Sciences (or Gilead Sciences' representative) for return of unused study drug supplies.

If IMP is destroyed on site, the investigator must maintain accurate records for all IMPs destroyed. Upon study completion, copies of the IMP accountability records must be filed at the site. Another copy will be returned to Gilead.

The study monitor will review IMP supplies and associated records at periodic intervals.

9.1.8. Inspections

The investigator will make available all source documents and other records for this trial to Gilead's appointed study monitors, to IRBs/IECs or to regulatory authority or health authority inspectors.

9.1.9. Protocol Compliance

The investigator is responsible for ensuring the study is conducted in accordance with the procedures and evaluations described in this protocol.

9.2. Sponsor Responsibilities

9.2.1. Protocol Modifications

Protocol modifications, except those intended to reduce immediate risk to study subjects, may be made only by Gilead. The investigator must submit all protocol modifications to the IRB/IEC in accordance with local requirements and receive documented IRB/IEC approval before modifications can be implemented.

9.2.2. Study Report and Publications

A clinical study report (CSR) will be prepared and provided to the regulatory agency(ies). Gilead will ensure that the report meets the standards set out in the ICH Guideline for Structure and Content of Clinical Study Reports (ICH E3). Note that an abbreviated report may be prepared in certain cases.

Investigators in this study may communicate, orally present, or publish in scientific journals or other scholarly media only after the following conditions have been met:

- The results of the study in their entirety have been publicly disclosed by or with the consent of Gilead in an abstract, manuscript, or presentation form or the study has been completed at all study sites for at least 2 years
- The investigator will submit to Gilead any proposed publication or presentation along with the respective scientific journal or presentation forum at least 30 days before submission of the publication or presentation.
- No such communication, presentation, or publication will include Gilead's confidential information (see Section 9.1.4).
- The investigator will comply with Gilead's request to delete references to its confidential information (other than the study results) in any paper or presentation and agrees to withhold publication or presentation for an additional 60 days in order to obtain patent protection if deemed necessary.

9.3. Joint Investigator/Sponsor Responsibilities

9.3.1. Payment Reporting

Investigators and their study staff may be asked to provide services performed under this protocol, eg, attendance at Investigator's Meetings. If required under the applicable statutory and regulatory requirements, Gilead will capture and disclose to Federal and State agencies any expenses paid or reimbursed for such services, including any clinical trial payments, meal, travel expenses or reimbursements, consulting fees, and any other transfer of value.

9.3.2. Access to Information for Monitoring

In accordance with regulations and guidelines, the study monitor must have direct access to the investigator's source documentation in order to verify the accuracy of the data recorded in the eCRF.

The monitor is responsible for routine review of the eCRF at regular intervals throughout the study to verify adherence to the protocol and the completeness, consistency, and accuracy of the data being entered on them. The monitor should have access to any subject records needed to verify the entries on the eCRF. The investigator agrees to cooperate with the monitor to ensure that any problems detected through any type of monitoring (central, on site) are resolved.

9.3.3. Access to Information for Auditing or Inspections

Representatives of regulatory authorities or of Gilead may conduct inspections or audits of the clinical study. If the investigator is notified of an inspection by a regulatory authority the investigator agrees to notify the Gilead Study Director immediately. The investigator agrees to provide to representatives of a regulatory agency or Gilead access to records, facilities, and personnel for the effective conduct of any inspection or audit.

9.3.4. Study Discontinuation

Both the sponsor and the investigator reserve the right to terminate the study at any time. Should this be necessary, both parties will arrange discontinuation procedures and notify the appropriate regulatory authority(ies), IRBs, and IECs. In terminating the study, Gilead and the investigator will assure that adequate consideration is given to the protection of the subjects' interests.

Appendix 2. Study Procedures Table

Period	Screening	Treatment										Follow-Up	
		1	2	3	4	5	6	7	8	9	10	PTx ^a	ET
Visit	1	0	2	4	6	10	14	18	20	24			
Week													
Study Day	-30 to -1	1	15	29	43	71	99	127	141	169			
Visit Window (±)			±3	±3	±3	±2	±3	±3	±5	±5	±3		
Written Informed Consent	X												
Medical History & Demographics	X												
Crohn's Disease & Treatment History	X												
12-lead ECG	X					X							X ^b
Review of Inclusion/Exclusion Criteria	X	X											
Physical Exam (Complete including perianal) ^c	X												
Physical Exam (symptom-based) and perianal assessment ^c		X	X	X	X	X	X	X		X	X	X	
Vital Signs	X	X	X	X	X	X	X	X		X	X	X	
Weight	X	X	X	X	X	X	X	X		X	X	X	
Height	X												
Adverse Events	X	X	X	X	X	X	X	X		X	X	X	
Concomitant Medications	X	X	X	X	X	X	X	X		X	X	X	
Randomization		X											
Study Drug Dispensing		X		X		X	X	X					
CCI													
CCI													
eDiary instruction & review ^e	X	X	X	X	X	X	X	X		X			
Flexible Sigmoidoscopy ^o	X									X			X ^r
MRI ^f	X									X			X ^s

Period	Screening	Treatment									Follow-Up		
		1	2	3	4	5	6	7	8	9	10	PTx ^a	ET
Visit													
Week			0	2	4	6	10	14	18	20	24		
Study Day	-30 to -1	1	15	29	43	71	99	127	141	169			
Visit Window (±)			±3	±3	±3	±2	±3	±3	±5	±5	±3		
Stool for C. diff toxin, pathogenic E. coli , Salmonella , Shigella , Campylobacter and Yersinia testing	X												
Stool O&P	X												
CCI													
Fecal Lactoferrin, Calprotectin	X										X		
Urine drug screen ^g	X												
Urinalysis ^q	X										X		
Pregnancy Test ^h	X	X		X	X	X	X	X	X	X	X	X	
TB screening ⁱ	X												
Chest x-ray ^q	X												
HBV, HCV, HIV screening ^j	X												
Hematology	X	X	X	X	X	X	X	X		X	X	X	
Chemistry	X	X	X	X	X	X	X	X		X	X	X	
Fasting Lipids ^p		X				X					X		
CRP	X	X	X	X	X	X	X	X		X	X	X	
Blood TCR/BCR repertoire sample ^k		X		X		X					X		
Plasma biomarker sample		X		X		X					X		
Serum biomarker sample		X		X		X					X		
Blood transcriptome sample		X		X		X					X		
CCI													
Serum immunoglobulin		X		X		X				X	X	X	
CCI													

Period	Screening	Treatment									Follow-Up	
Visit	1	2	3	4	5	6	7	8	9	10	PTx ^a	ET
Week		0	2	4	6	10	14	18	20	24		
Study Day	-30 to -1	1	15	29	43	71	99	127	141	169		
Visit Window (±)			±3	±3	±3	±2	±3	±3	±5	±5	±3	

CCI
CCI

a The Post-Treatment (PTx) visit should occur 30 days after the last dose of study drug. Only subjects who roll over into the LTE study will not complete PTx assessments.

b For subjects who terminate prior to Week 10

c A complete physical examination (PE) including; vital signs, body weight, height, and perianal assessment (including completion of the Perianal Fistula Assessment Worksheet) will be performed at screening. A symptom-directed PE and perianal assessment(including completion of the Perianal Fistula Assessment Worksheet) should be performed at all other time points.

e Subjects should begin filling out the eDiary the day of their initial screening visit and continue to fill it out throughout the remainder of the study.

f Refer to Section 6.6 for details on the MRI procedure

g Positive cocaine test disqualifies subject; positive amphetamines, barbiturates, benzodiazepines, and opioids require medical monitor review

h All females meeting the childbearing potential criteria must have a serum pregnancy testing at screening and a urine pregnancy test must be completed every 4 weeks at a minimum. If any pregnancy test is positive, study drug must be immediately interrupted and the subject should come to the site for serum pregnancy test in clinic.

i Proof of no active or untreated latent TB at screening. Subjects who are diagnosed with latent TB at screening must initiate an adequate course of prophylaxis as per local standard of care, for a minimum of 4 weeks prior to randomization. Subject may initiate study drug dosing only after consultation with the Study Medical Monitor.

j An HIV-1/HIV-2 antibody test, a HCV antibody test, a HBV surface antigen test, a HBV surface antibody test, and a HBV core antibody test will be performed on all subjects. Subjects with positive HBcAb require reflex testing for HBV DNA (conducted locally). Refer to section 6.11.1.2 for further details.

k TCR: T-cell receptor; BCR: B-cell receptor

l Refer to Section 6.5 for details on the flexible sigmoidoscopy procedure

[figure not shown]
m Subjects should fast (no food or drinks, except water) for at least 8 hours prior to blood sample collection at Day 1, Week 10, and Week 24

n Chest x-ray (views as per local guidelines) taken at screening or within the 3 months prior to screening (with the report or films available for investigator review) without evidence of active or latent TB infection

o Subjects meeting non-response or disease worsening criteria should undergo a flexible sigmoidoscopy assessment prior to exiting the study.

p Subjects meeting non-response or disease worsening criteria should undergo a pelvic MRI prior to exiting the study.

Appendix 3. Management of Clinical and Laboratory Adverse Events

CCI

Appendix 5. Simple Endoscopic Score for Crohn's Disease (SES-CD)

Variables	Score			
	0	1	2	3
Size of ulcers (cm)	None	Aphthous ulcers (diameter 0.1-0.5)	Large ulcers (diameter >0.5-2)	Very large ulcers (diameter > 2)
Ulcerated Surface (%)	None	< 10	10-30	> 30
Affected surface (%)	Unaffected segment	< 50	50-75	> 75
Presence of narrowings	None	Single, can be passed	Multiple, can be passed	Cannot be passed

Total SES-CD: sum of the values of the 4 variables for the 5 bowel segments. Values are given to each variable and for every examined bowel segment (eg, rectum, left colon, transverse colon, right colon, and ileum); note Total SES-CD will not be calculated during Study GS-US-419-4016

{Daperno 2004}

For Study GS-US-419-4016, the Proctitis SES-CD score (which includes an overall assessment of both rectum and anal canal) and Anal Canal Segmental SES-CD score will only score **size of ulcers** and **ulcerated surface**. The Proctitis SES-CD score will be used to provide an endoscopic measure of proctitis. CCI

CCI

Appendix 8. CTCAE Grading Scale for Severity of Adverse Events

Please refer to the Common Terminology Criteria for Adverse Events (CTCAE) Version 4.03, which can be found at:

http://evs.nci.nih.gov/ftp1/CTCAE/CTCAE_4.03_2010-06-14_QuickReference_8.5x11.pdf

For AEs associated with laboratory abnormalities, the event should be graded on the basis of the clinical severity in the context of the underlying conditions; this may or may not be in agreement with the grading of the laboratory abnormality.

The only modification to the CTCAE criteria is the addition of a Grade 1 upper respiratory infection as follows:

CTCAE v4.0 Term	Grade 1	Grade 2	Grade 3	Grade 4	Grade 5	CTCAE v4.03 AE Term Definition
Upper respiratory infection	Mild symptoms; symptomatic relief (eg, cough suppressant, decongestant)	Moderate symptoms; oral intervention indicated (eg, antibiotic, antifungal, antiviral)	IV antibiotic, antifungal, or antiviral intervention indicated; radiologic, endoscopic, or operative intervention indicated	Life-threatening consequences; urgent intervention indicated	Death	A disorder characterized by an infectious process involving the upper respiratory tract (nose, paranasal sinuses, pharynx, larynx, or trachea).

Appendix 9. Pregnancy Precautions, Definition for Female of Childbearing Potential, and Contraceptive Requirements

The administration of filgotinib in embryo-fetal animal development studies resulted in decreased numbers of viable rat fetuses, increased resorptions, and visceral and skeletal malformations. Similar effects were noted in the rabbit. A safety margin relative to human exposure has not been identified. Pregnancy is contraindicated during use of filgotinib.

For participation in this study, the use of *highly effective* contraception is required as outlined below for all subjects who are of childbearing potential. In addition, during the study women of childbearing potential must have at minimum, a urine pregnancy test every 4 weeks.

1) Definitions

a) Definition of Childbearing Potential

For the purposes of this study, a female-born subject is considered of childbearing potential following the initiation of puberty (Tanner stage 2) until becoming post-menopausal, unless permanently sterile or with medically documented ovarian failure. Women who do not meet below criteria for being post-menopausal, are not permanently sterile, or do not have medically documented ovarian failure must have pregnancy testing as outlined by the protocol.

Women are considered to be in a postmenopausal state when they are ≥ 54 years of age with cessation of previously occurring menses for ≥ 12 months without an alternative cause.

Permanent sterilization includes hysterectomy, bilateral oophorectomy, or bilateral salpingectomy in a female subject of any age. Bilateral tubal ligation is not considered permanent sterilization.

b) Definition of Male Fertility

For the purposes of this study, a male-born subject is considered fertile after the initiation of puberty unless permanently sterilized by bilateral orchidectomy or has medical documentation of permanent male infertility. Vasectomy is not considered permanent sterilization.

2) Contraception for Female Subjects

a) Study Drug Effects on Pregnancy and Hormonal Contraception

Filgotinib is contraindicated in pregnancy as there is a possibility of human teratogenicity/fetotoxicity in early pregnancy based on non-clinical data. Data from a drug-drug interaction study of filgotinib and hormonal contraceptives (GS-US-417-3916) have demonstrated co-administration with filgotinib did not alter the pharmacokinetics of representative hormonal contraceptives levonorgestrel/ethinyl estradiol.

Please refer to the latest version of the filgotinib IB for additional information.

b) Contraception for Female Subjects of Childbearing Potential

The inclusion of female subjects of childbearing potential requires the use of highly effective contraceptive measures. Women must have a negative serum pregnancy test at screening and a negative urine pregnancy test on the Day 1 visit prior to randomization. Pregnancy tests will be performed at monthly intervals thereafter. In the event of a delayed menstrual period (> one month between menstruations), a pregnancy test must be performed to rule out pregnancy. This is true even for women of childbearing potential with infrequent or irregular periods.

Female subjects must agree to use one of the following methods from screening until 35 days following the last dose of study drug.

- Complete abstinence from intercourse of reproductive potential. Abstinence is an acceptable method of contraception only when it is in line with the subject's preferred and usual lifestyle.

Or

- Consistent and correct use of 1 of the following methods of birth control listed below.

Intrauterine device (IUD) with a failure rate of < 1% per year

Tubal sterilization

Essure micro-insert system (provided confirmation of success 3 months after procedure)

Vasectomy in the male partner (provided that the partner is the sole sexual partner and had confirmation of surgical success 3 months after procedure)

- Female subjects, who wish to use a hormonally based method, must use it in conjunction with a barrier method; the barrier method is to be used either by the female subject or by her male partner. Female subjects who utilize a hormonal contraceptive as one of their birth control methods must have consistently used the same method for at least three months prior to study dosing. Hormonally-based contraceptives and barrier methods permitted for use in this protocol are as follows:

Hormonal methods (each method *must* be used with a barrier method, preferably male condom)

- Oral contraceptives (either combined estrogen/progestin or progesterone only)
- Injectable progesterone
- Implants of levonorgestrel
- Transdermal contraceptive patch
- Contraceptive vaginal ring

Barrier methods (each method *must* be used with a hormonal method)

- Male or female condom with or without spermicide
- Diaphragm with spermicide
- Cervical cap with spermicide
- Sponge with spermicide

All female subjects must also refrain from egg donation and in vitro fertilization during treatment and until at least 35 days after the last study drug dose.

3) Contraception Requirements for Male Subjects

It is theoretically possible that a relevant concentration of study drug may be achieved in a female partner from exposure to the male subject's seminal fluid. Therefore, male subjects with female partners of childbearing potential must use condoms during study participation and for 90 days after the last study drug dose. Female partners of male study subjects should consider using one of the above methods of contraception as well. Male subjects must also refrain from sperm donation during treatment and until at least 90 days after the end of study drug dosing.

4) Unacceptable Birth Control Methods

Birth control methods that are unacceptable include periodic abstinence (eg, calendar, ovulation, symptothermal, post-ovulation methods), withdrawal (coitus interruptus), spermicides only, and lactational amenorrhea method (LAM). Female condom and male condom should not be used together.

5) Procedures to be Followed in the Event of Pregnancy

Subjects will be instructed to notify the investigator if they become pregnant at any time during the study, or if they become pregnant within 30 days of last study drug dose. Subjects who become pregnant or who suspect that they are pregnant during the study must report the information to the investigator and discontinue study drug immediately. Subjects whose partner has become pregnant or suspects she is pregnant during the study are to report the information to the investigator.

Instructions for reporting pregnancy, partner pregnancy, and pregnancy outcome are outlined in Section [7.7.2.1](#).

6) Pregnancy Testing

All females of childbearing potential will have urine pregnancy testing every 4 weeks (in clinic) during their study participation. If a urine pregnancy test is positive, the subject should stop study drug immediately, contact the investigator, and have a confirmatory serum pregnancy test in clinic.

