4.3. Exclusion Criteria

Subjects who meet *any* of the following exclusion criteria are not to be enrolled in this study.

- 1) Pregnant or lactating females.
- 2) Males and females of reproductive potential who are unwilling to adhere to contraceptive guidance as outlined by [Appendix 9](#).
- 3) Females who may wish to become pregnant and/or plan to undergo egg donation or egg harvesting for the purpose of current or future fertilization during the course of the study and up to 35 days after the last dose of the study drug.
- 4) Male subjects unwilling to refrain from sperm donation during the study and for at least 90 days after the last dose of study drug.
- 5) Known hypersensitivity to filgotinib, its metabolites, or formulation excipients
- 6) Claustrophobia to a degree that prevents tolerance of MRI scanning procedure (sedation is permitted at discretion of investigator).
- 7) Metallic implant of any sort that prevents MRI examination, not limited to but including aneurysm clips, metallic foreign body, vascular grafts or cardiac implants, neural stimulator, metallic contraceptive device, body piercing that cannot be removed, cochlear implant; or other contraindication to MRI examination.
- 8) Known hypersensitivity to gadolinium
- 9) Currently have complications of CD as any of the following:
 - a) Symptomatic strictures, OR
 - b) Severe (impassable) rectal/anal stenosis, OR
 - c) Short bowel syndrome, OR
 - d) Any other complications which could preclude the use of the CDAI to assess response to therapy, or would possibly confound the evaluation of benefit from treatment with filgotinib
- 10) Presence of current rectovaginal, anovaginal, or enterovesicular fistulae
- 11) Has an abscess > 2 cm or an abscess that the Investigator feels requires drainage based on either clinical assessment or MRI, unless drained and treated at least 4 weeks prior to Day 1, and are not anticipated to require surgery during the study
- 12) Has a CDAI score > 300

- 13) History of major surgery or trauma within 30 days prior to screening
- 14) Presence of ulcerative colitis (UC), indeterminate colitis, ischemic colitis, fulminant colitis, or toxic mega-colon
- 15) History of total proctocolectomy, total colectomy, presence of ileostomy or colostomy, or likely requirement for surgery during the study
- 16) Dependence on parenteral nutrition
- 17) History or evidence of incompletely resected colonic mucosal dysplasia

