7.7.2. Instructions for Reporting Special Situations

7.7.2.1. Instructions for Reporting Pregnancies

The investigator should report pregnancies in female study subjects that are identified after initiation of study drug and throughout the study, including the post study drug follow-up period, to the Gilead PVE using the pregnancy report form within 24 hours of becoming aware of the pregnancy.

Refer to Section 7.3 and the eCRF completion guidelines for full instructions on the mechanism of pregnancy reporting.

The pregnancy itself is not considered an AE nor is an induced elective abortion to terminate a pregnancy without medical reasons.

Any premature termination of pregnancy (eg, a spontaneous abortion, an induced therapeutic abortion due to complications or other medical reasons) must be reported within 24 hours as an SAE. The underlying medical reason for this procedure should be recorded as the AE term.

A spontaneous abortion is always considered to be an SAE and will be reported as described in Section 7.3.2. Furthermore, any SAE occurring as an adverse pregnancy outcome post study must be reported to Gilead PVE.

The subject should receive appropriate monitoring and care until the conclusion of the pregnancy. The outcome should be reported to Gilead PVE using the pregnancy outcome report form. If the end of the pregnancy occurs after the study has been completed, the outcome should be reported directly to Gilead PVE. Gilead PVE contact information is as follows:

Gilead PVE:	Fax:	PPD
	E-mail:	PPD

Pregnancies of female partners of male study subjects exposed to Gilead or other study drugs must also be reported and relevant information should be submitted to Gilead PVE using the pregnancy and pregnancy outcome forms within 24 hours. If the end of the pregnancy occurs after the study has been completed, the outcome should be reported directly to Gilead PVE.

Gilead PVE:	Fax:	PPD
	E-mail:	PPD

Refer to Appendix 9 for Pregnancy Precautions, Definition for Female of Childbearing Potential, and Contraceptive Requirements.

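### Subject instructions for notifying pregnancies (30 days for women, an undefined study period for partners of men) do not match the protocol's own 35- and 90-day precaution periods

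*Protocol*

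**What the plan says.** **What subjects are told to notify.** Appendix 9, item 5 covers a female subject's own pregnancy if it begins during the trial "or if they become pregnant within 30 days of last study drug dose". A separate sentence covers male subjects: "Subjects whose partner has become pregnant or suspects she is pregnant during the study are to report the information to the investigator". It names no number of days after the last dose.

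**The precaution periods.** Appendix 9, item 2b says: "Female subjects must agree to use one of the following methods from screening until 35 days following the last dose of study drug". Egg donation and in vitro fertilization are barred "until at least 35 days after the last study drug dose", and exclusion criterion 3 in Section 4.3 runs "up to 35 days after the last dose of the study drug". Under item 3, men whose partners could conceive "must use condoms during study participation and for 90 days after the last study drug dose". The reason given is possible transfer in seminal fluid: "It is theoretically possible that a relevant concentration of study drug may be achieved in a female partner".

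**What investigators must report.** Section 7.7.2.1 sets the duty for pregnancies identified in female subjects "throughout the study, including the post study drug follow-up period". Partner pregnancies must also go to the sponsor's pharmacovigilance group within 24 hours, and no end date is stated.

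**When contact ends.** Section 6.13 places the post-treatment visit, with its pregnancy test, 30 days after the last dose. Section 3.9 defines End of Study at trial level, 30 days after the last subject's last dose. Section 5.4, on recording medication, uses end of study in a per-subject sense, also at 30 days.

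**The concern.** A period of required contraception and a period of required notification should normally end together. If notification ends first, a contraceptive failure in the remaining days is one that nobody has been asked to mention.

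The protocol gives reason to care. Section 1.2.2.4 reports embryo lethality and teratogenicity in rats and rabbits, with the teratogenicity at exposures similar to or slightly above human exposure at 200 mg. Appendix 9 opens by saying that no safety margin relative to human exposure has been identified. Section 1.5 names contraception as the mitigation. Pregnancies that occur despite it are therefore informative even if very few are expected among about 75 subjects.

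Only safety information is at stake. No efficacy analysis is touched, and Section 7.6 of the SAP plans nothing beyond a listing of subjects who become pregnant during the study.

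**Working it through.** The plan states no figure to reproduce. The check compares day counts, with day 0 as the last dose.

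| | Precaution ends | Subject told to notify until | Investigator must report until |
|---|---|---|---|
| Female subject | day 35 (App. 9 item 2b; exclusion 3) | conception by day 30 (App. 9 item 5) | end of post-treatment follow-up, day 30 (7.7.2.1 with 6.13) |
| Partner of male subject | day 90 (App. 9 item 3) | end of the study, undefined (App. 9 item 5) | no end date (7.7.2.1) |

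**Women.** Gap = 35 − 30 = 5 days, that is days 31 to 35. Section 7.7.2.1 does not close it. Its duty covers pregnancies identified up to the end of follow-up, and a conception on days 31 to 35 cannot have been identified by day 30. The last scheduled pregnancy test is at that visit, so self-report is the only route left, and the instruction to self-report has already ended.

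**Partners of men.** The result depends on when the study ends for this purpose.

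1. *The subject's own 30-day visit.* Section 5.4's usage fits this. Gap = 90 − 30 = 60 days, that is days 31 to 90.
2. *Trial-level End of Study (Section 3.9).* Let *d* be the number of days from this man's last dose to the last subject's last dose. End of Study then falls on his day *d* + 30, and the gap is max(0, 90 − (*d* + 30)) = max(0, 60 − *d*). With *d* = 0 the gap is 60 days, with *d* = 30 it is 30 days, and with *d* of 60 or more it is 0.
3. *Section 7.7.2.1 alone.* The investigator's duty has no cut-off, so the formal reporting gap is 0 days. What remains is that men are not told to notify after the study, and no contact after day 30 is scheduled at which the investigator would learn of a pregnancy.

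**Who is affected.** Subjects who enter the extension may continue study drug there and skip the post-treatment visit (Sections 3.2 and 6.13). The point concerns those who do not enter it.

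**The case against.** The strongest reply is that this is a small wording mismatch with several backstops. The 30-day notification matches the adverse event window in Section 7.3.1 and the post-treatment visit. Section 7.7.2.1 also requires reporting of serious adverse pregnancy outcomes arising after the study. Congenital anomaly is a serious adverse event under Section 7.1.2. Section 7.3.2 asks investigators to report later serious events that they learn of and judge relevant to study drug. All of this stands, and it limits the consequence. But these routes concern serious outcomes, not pregnancies as such, and they depend on the investigator hearing of the case.

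Several stronger readings are tempting, and the documents do not support them:

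- *That partner pregnancies are also cut off at 30 days.* The 30-day phrase concerns subjects who themselves become pregnant. The partner sentence has no day count.
- *That partner pregnancies after the study need not be reported and are lost.* Section 7.7.2.1 requires their reporting without an end date, and item 5 itself refers the reader there.
- *That men's gap is simply 60 days.* That holds on one reading of when the study ends. On the trial-level reading it runs from 0 to 60.
- *That the protocol regards every conception within 35 or 90 days as exposed.* These are precaution periods. Only the male period carries an exposure reason, and it is called theoretical. No such reason is given for the 35 days.
- *That embryo lethality was seen near the 200 mg exposure.* Section 1.2.2.4 ties teratogenicity to that exposure, and Section 1.5 ties malformations to it.

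**Conclusion.** The inconsistency is real. For women who do not enter the extension, the notification instruction falls 5 days short of the contraception period, and the 30-day follow-up does not make up the difference. This follows from stated day counts, taking the post-treatment visit at day 30.

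For men the finding is narrower. The investigator's duty is open-ended, but the instruction to the subject stops at an undefined point: 60 days short of the condom period on the per-subject reading, and 0 to 60 days short on the trial-level reading. The text does not settle which applies, which is itself a reason to reconcile it.

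The documents give no pregnancy rate, so the number of pregnancies that might be missed cannot be estimated. It is likely to be very small. The point merits correction because the animal findings make each case informative and the remedy is cheap. It does not threaten any planned analysis.

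**What to change.** Reconcile Appendix 9, items 2, 3 and 5, with Section 7.7.2.1. State an explicit end date, counted from the last dose, for subject notification of (a) a female subject's own pregnancy and (b) a partner's pregnancy, each agreeing with the precaution period stated for that group. Say whether the limit runs on conception, as item 5 is worded, or on identification, as Section 7.7.2.1 is worded for female subjects. Replace the reference to the study in the partner sentence with a defined endpoint, and carry the same text into the consent form. Which length is right is a clinical matter for the sponsor, and this review proposes none.

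The cost is protocol and consent wording, with no added visits or tests. If the agreed periods run past day 30, subjects will be asked to self-report after their last scheduled contact, and for men dosed late in the trial possibly after End of Study. Sites therefore need to keep a route open for such reports. Section 7.7.2.1 already has one for pregnancy outcomes after study completion.
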